VA Office of Research and Development Results Record C0239-R

Title: Randomized Trial Comparison of Ototoxicity Monitoring Programs

ClinicalTrials.gov identifier: NCT02099786

Protocol; Document Date: 9-29-17

Experimental Methods

A. Subjects.

A1. Subject Recruitment: An estimated 320 patients from VA Portland Health Care System (VAPORHCS) receiving chemotherapy will be identified by a search of the upcoming chemotherapy unit appointment list, pharmacy list or by oncology referral including verbal referral and encrypted email. Additionally, approximately 120 healthy control subjects (Veterans and non-Veterans) not administered chemotherapy will also be recruited at the VAPORHCS from posted recruitment advertisements and from the NCRAR database of Veterans willing to participate in future hearing research projects. Potential chemotherapy patients will be accessed using electronic medical records (CPRS) to determine the diagnosis and treatment plan and to search for exclusionary criteria. If the potential subject is not excluded based on initial CPRS search, oncology personnel will approach the potential subject to determine his/her willingness to learn more about the study after hearing a brief description. The Program Evaluation (PE) audiologist will then talk with the patient, offer a more thorough explanation of the study, including the necessity for duplicate testing. If the potential subject remains interested in the project, informed consent will be obtained including an explanation of the goals of the study, requirements of the study protocol and the potential risks and benefits to the subject.

Initial testing to establish inclusion in the study and to provide the first PE will be done in a quiet area. After the evaluation, if the subject has met all further inclusion criteria, the subject will be randomized to a treatment arm: Standard of care (SOC) or Comprehensive Ototoxicity Monitoring Program for VA healthcare (COMP-VA). Study personnel will then be informed that a subject has been consented, tested, and assigned to a study arm and is ready to receive a baseline evaluation.

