VA Office of Research and Development Results Record C0239-R

Title: Randomized Trial Comparison of Ototoxicity Monitoring Programs

ClinicalTrials.gov identifier: NCT02099786

Outcomes and Statistical Plan; Document Date: 9-29-17

Outcomes and Statistical Plan

Outcome Measures

The following outcomes were evaluated as a function of treatment arm.

1. **Hearing tests.** Rates of ototoxicity were evaluated using two criteria: (i) Ototoxic hearing shifts meeting the ASHA 1994 definition 20dB shift at one frequency; 10 dB shift at two consecutive frequencies or loss of response at three frequencies. (ii) Ototoxicity meeting the Cancer Institute Common Terminology Criteria for Adverse Events (CTCAE) Grade 1 or greater toxicity [hearing shift of 15-25 dB averaged at 2 contiguous test frequencies in at least one ear].
2. **Audiology rehabilitation service use.** This included: (i) service utilization to issue new hearing aids to subjects who were not hearing aid users at baseline; and (ii) technology update or hearing aid adjustment for previous hearing aid users. CPRS progress notes were monitored by the NCRAR Research Audiologist on each subject enrolled in the study in order to determine audiology rehabilitation service use for one year post-randomization. All audiology clinic visits were recorded by date and type of visit. Additionally, subjects were queried about aural rehabilitation service at each PE and interim phone calls.
3. **Quality of life measures.** Differences in the HHIA questionnaire score (or HHIE score as appropriate depending on the age of the subject) at PE 3 were evaluated.
4. **Survivorship** among subjects was also evaluated, defined as differences in rates of death during the study period.

Hypotheses to be Tested and Statistical Plan

1. *Use of COMP-VA will improve patients' hearing and quality of life outcomes without diminishing chances for survival.* Simple analysis will entail computing odds ratios and contrasting these between the COMP-VA and SOC groups. We will also fit a logistic regression model to the probability of ototoxicity (separately modeled for ASHA and CTCAE grade 1 or

greater) with randomization group assignment as predictor. *We anticipate that hearing loss progression will be less among COMP-VA subjects, meaning that, the COMP-VA group will have smaller 35 day and 1 year post-randomization hearing shifts compared to SOC patients.*

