2. *We hypothesize that COMP-VA will minimize some of the adverse effects of cisplatin treatment on Veterans' hearing-related quality of life, either through treatment modifications to diminish cisplatin-induced hearing loss or effective post-chemo audiological service delivery to limit the ill-effects of any pre-existing, new or worsened communication deficit.* We will conduct a contrast of perceived hearing handicap (HHIE or HHIA questionnaire administered at 1 year post-randomization), between patients randomized to COMP-VA and SOC. We will conduct a t-test with randomization arm as the contrast to test the importance of COMP-VA on perceived quality of life outcomes.

3. *Compared with patients randomized to SOC, patients randomized to COMP-VA will use Audiology rehabilitation services at a higher rate because of their greater awareness of new, increased or pre-existing communication deficits.* To test this hypothesis, we will contrast the probability of one or more audiology clinic rehabilitation visits using logistic regression with group membership as a factor.

4. *We anticipate that cisplatin patients given the COMP-VA intervention will fair no worse than SOC patients in terms of their survival.* This component of the study is framed as a non-inferiority trial. i.e. we require sufficient evidence to reject the null hypothesis that COMP-VA patients have lower one-year survival rates than patients treated under SOC. Analysis for non-inferiority trials using survival outcomes have been described and are easily computed using logistic regression output. We will require a non-inferiority margin of no more than 1.1 mortality odds among COMP-VA patients relative to SOC patients. From an analytical

perspective this means that the upper 95% confidence bound for the fitted odds ratio must be less than 1.1 to reject the null hypothesis that COMP-VA induces extra mortality risks.

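### Rehabilitation-service endpoint: the event differs by baseline hearing-aid use, but the test pools users and non-users with arm as the only named factor; adding the baseline term and reporting both components is a low-cost gain

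*SAP*

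**What the plan says.** SAP Outcome Measures item 2 lists two kinds of service, set by the patient's status at entry. The first is "service utilization to issue new hearing aids to subjects who were not hearing aid users at baseline". The second is "technology update or hearing aid adjustment for previous hearing aid users". Progress notes are followed "in order to determine audiology rehabilitation service use for one year post-randomization", and the SAP adds: "All audiology clinic visits were recorded by date and type of visit".

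Item 3 of the hypotheses section predicts higher use under COMP-VA "because of their greater awareness of new, increased or pre-existing communication deficits". Its test is a logistic regression on a single yes/no outcome: "we will contrast the probability of one or more audiology clinic rehabilitation visits using logistic regression with group membership as a factor".

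Neither document names a baseline hearing-aid term, an interaction, a component analysis, or stratification of the randomisation by hearing-aid use. Neither gives a share of users, a visit rate, a target effect, a significance level or a power figure for this hypothesis.

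**The concern.** A first fitting and an adjustment of an existing aid are different events and may well occur at different rates. If they do, baseline status predicts the outcome strongly, and leaving it out of the model gives up precision. It also leaves the estimate of this particular trial exposed to chance imbalance in the number of users per arm.

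Interpretation is affected as well. One pooled odds ratio cannot show whether COMP-VA led patients without aids to obtain them, changed how often existing users came back, or both. Hypothesis 3 rests on awareness of both new and pre-existing deficits, so the reader will want to see both.

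**Working it through.** The plan has no power figure for this test, so there is nothing to reproduce. The check brackets the possible loss.

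**Inputs from the documents.** Protocol A1 has two arms and states: "An estimated 320 patients from VA Portland Health Care System (VAPORHCS) receiving chemotherapy will be identified by a search". These are patients identified; the number randomised is not given. I take N = 320 as the upper case and 240 as a sensitivity value.

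**Assumptions.** Allocation 1:1; two-sided 5% level; share of users q = 30% (also 10% and 40%); SOC event rate 10–20% in non-users (p_n) and 20–80% in users (p_u); odds ratio (OR) 2 in non-users and 1, 2 or 3 in users.

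**Step 1, COMP-VA rate in each group:** p′ = OR·p / (1 − p + OR·p).
- Non-users at 20%: 0.40/1.20 = 0.3333.
- Users at 70%: 1.40/1.70 = 0.8235.

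**Step 2, pooled rates.**
- SOC: P0 = 0.7×0.20 + 0.3×0.70 = 0.3500.
- COMP-VA: P1 = 0.7×0.3333 + 0.3×0.8235 = 0.4804.
- Pooled OR = (0.4804/0.5196)/(0.3500/0.6500) = 1.72, although the OR is 2 in each group.

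**Step 3, power of the arm-only test,** n = 160 per arm, with P̄ the mean of P0 and P1:
Φ{[(P1 − P0)√n − 1.96√(2P̄(1 − P̄))] / √(P0(1 − P0) + P1(1 − P1))} = Φ{(1.649 − 1.366)/0.691} = Φ(0.41) = 65.9%.

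**Step 4, power stratified by baseline status,** with m per arm in each stratum and p̄ the mean of p and p′:
D = Σ(m/2)(p′ − p), V0 = Σ(m/2)p̄(1 − p̄), V1 = Σ(m/4)[p(1 − p) + p′(1 − p′)], power = Φ{(D − 1.96√V0)/√V1}.
- Non-users, m = 112: 7.467, 10.951, 10.702.
- Users, m = 48: 2.965, 4.356, 4.264.
- Totals: D = 10.431, V0 = 15.307, V1 = 14.966. Power = Φ{(10.431 − 7.668)/3.869} = Φ(0.71) = 76.2%.

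**Step 5, the range (N = 320, 30% users).**

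| SOC rate, non-users / users | OR, non-users / users | Pooled OR | Power, arm only | Power, with baseline term | Gain (points) |
|---|---|---|---|---|---|
| 20% / 20% | 2 / 2 | 2.00 | 77.2% | 77.2% | 0 |
| 20% / 50% | 2 / 2 | 1.87 | 76.3% | 80.2% | 4 |
| 20% / 70% | 2 / 2 | 1.72 | 65.9% | 76.2% | 10 |
| 10% / 80% | 2 / 2 | 1.45 | 34.8% | 56.8% | 22 |
| 20% / 70% | 2 / 1 | 1.48 | 39.9% | 46.3% | 6 |
| 20% / 50% | 2 / 3 | 2.07 | 87.9% | 91.5% | 4 |

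With N = 240 the first four gains are 0, 4, 10 and 18 points. In the 10%/80% row, at N = 320, the gain is 12 points with 10% users and 24 with 40% users.

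In the last two rows, testing non-users alone would have 61.8% power. That beats the pooled test if users do not respond, and is far worse if they respond more strongly.

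**Step 6, check by simulation** (1,500 trials per scenario, logistic regression). In the worked case, power was 66.3% and 76.4%, against 65.9% and 76.2% by formula. The type I error of the arm-only test was 4–6% throughout. With no effect in users, the adjusted model returned an average OR of 1.62, which describes neither group.

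**Step 7, chance imbalance.** Take 35% users and rates of 70% and 20% with no treatment effect. If one arm has 40% users and the other 30%, the event rates are 0.4×0.70 + 0.6×0.20 = 0.40 and 0.3×0.70 + 0.7×0.20 = 0.35. The apparent OR is (0.40/0.60)/(0.35/0.65) = 1.24. The standard deviation of the difference is √(2×0.35×0.65/160) = 5.3 points, so a 10-point gap is about 1.9 SD.

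**The case against.** The strongest reply is that the planned analysis is a valid test of the hypothesis as written. Arm is randomised, the type I error holds, and chance imbalance is already covered by that error rate. The hypothesis names pre-existing deficits, so counting existing users is deliberate. If they respond well, pooling helps. The arm-only OR is also a legitimate marginal estimate. All of this stands.

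A reader might infer more: that pooling certainly dilutes the COMP-VA effect and certainly costs power, because routine maintenance visits let existing users meet the outcome easily. The documents do not support this. They give no visit rates and say nothing about routine visits. The list of services in the outcome definition is introduced as what was included, which is looser than a rule that a non-user counts only once aids are issued. With similar rates the loss is nil. With a common OR, the fall from 2 to 1.72 or 1.45 arises because odds ratios do not average across groups with different baseline rates; it is not a masked effect.

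It is also fair that a descriptive split stays possible without any change, since visits are logged by type. That does not replace a pre-specified analysis.

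**Conclusion.** The point holds as a conditional improvement in efficiency and interpretation. It does not show bias or an invalid test. The mismatch between the two-part outcome definition and the one-factor model is plain in the SAP. Its cost in power cannot be computed from the documents. Under the stated assumptions, with a common OR of 2, it is nil at equal rates, 4 to 10 points at moderate to marked differences, and about 20 points when rates are as far apart as 10% and 80%.

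True dilution requires COMP-VA to act less in existing users. The baseline term alone then recovers little (about 6 points in the case above), and separate estimates are needed to see what happened. In no scenario examined did adding the term lower power.

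**What to change.** In SAP item 3, add baseline hearing-aid use (yes/no, as of randomisation) as a factor beside arm. State that the adjusted arm effect in all randomised patients remains the single test of hypothesis 3. As supportive estimates, report the arm odds ratio separately for new aids in non-users and for update or adjustment in users, with the arm-by-status interaction.

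The change is one of wording. Scoring the outcome already requires baseline status. The measurement list in Protocol B1 does not mention it, however, so its capture before randomisation should be confirmed.

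There are two costs. First, the adjusted odds ratio is conditional on baseline status, not marginal, and should be labelled so; the unadjusted value can be shown beside it. Second, the component intervals will be wide. In the worked case (20%/70%, OR 2), the standard error of the log odds ratio in users is √(1/33.6 + 1/14.4 + 1/39.5 + 1/8.5) = 0.49, an expected 95% interval of about 0.76 to 5.2. In non-users it is √(1/22.4 + 1/89.6 + 1/37.3 + 1/74.7) = 0.31, or about 1.09 to 3.7. The component results should therefore be read as description, not as further tests.

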A2. Subject Exclusion Criteria: Subjects must be treated for cancer and must provide a reliable hearing test to be enrolled in the treatment arms of this study. Criteria for excluding subjects (chemotherapy and controls subjects) from this study are: 1) cognitively or physically unable to participate (patient or nurse report patient is incapable of participating), CPRS indication that subject exhibits aggressive behavior, subject has documented dementia, Alzheimer's disease, or severe psychosocial disorder, CPRS notes indicate individual is not legally capable of providing informed consent (subject has a legal guardian); 2) exhibits Meniere's disease or retrocochlear disorder based on hearing test results, patient report or notes in CPRS; 3) exhibits active or recent history of middle ear disorder based on otoscopy, tympanometry, patient report, or notes in CPRS; 4) unwilling to participate; and 6) hearing thresholds > 70 dB SPL at 4 kHz and below (control subjects only).

B. Experimental Techniques. Study measurements are divided into three general groups: Program Evaluation measurements, SOC measurements (Arm 1) and COMP-VA measurements (Arm 2). Measurements in non-clinical controls generally mirror those done for the COMP-VA arm. Testing is done by an Audiologist. The SOC protocol (Arm 1: SOC) is done according to the Audiology Service established protocol. The COMP-VA (Arm 2) protocol includes hearing testing at baseline and at each treatment interval along with a one-month post-treatment evaluation. Testing will be done using OtoID and/or the OtoID-Tablet and/or a standard audiometer. As part of this project, we have developed an updated version of the OtoID which involved migrating to a tablet-controlled device. Like all audiometers, this audiometer is not a medical device since it is "non-invasive" and, therefore, does not require FDA oversight or approval. Rather, the OtoID-Tablet properties are defined and calibrated according to the American National Standards Institute (ANSI) S3.6-2010 "Specification for Audiometers". It was calibrated in 2017 and will be calibrated annually, per ANSI standards.

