C2a. Distortion Product Otoacoustic Emission Instrumentation for COMP-VA: Either the OtoID-based DPOAE testing (or cart system) can be used to collect DPOAEs.

C3. Other data to be gathered on study participants with cancer: Additional information obtained on each subject from the electronic medical records (CPRS) will be entered into the database, maintained by by study team members including a biostatistician and research assistant(s). Information to be obtained will include patient factors such as name, gender, age, type of cancer and staging, drug treatment variables such as cisplatin dose and dosing (intensity) and concomitant radiation dose and doublet medication and other information related to treatment and patient factors as required to accomplish the study goals. CPRS clinical progress notes will be monitored by a study team member on each subject (estimated n=80/yr) entered into either study arm in order to obtain Audiology Service utilization **for up to one year** post-randomization. In addition, in order to get a less biased estimate of audiological services utilization rates, an historical cohort comprised of all patients identified as receiving cisplatin approximately 3 years prior to the initiation of the study will be searched in CPRS and the cancer registry for audiological services used (estimated n=220 pts). We estimate approximately 300 patient records may be accessed to complete this search. These data may be combined with data from other studies done by these investigators in an IRB-approved manner.

A study team member may request providers' feedback in the form of a simple checklist (Oncology Practitioner Survey) provided to them at each treatment interval by a study team member.

We may also survey practitioners (oncologists, nurses, and audiologists) to assess their beliefs about ototoxicity monitoring practices using an anonymous beliefs questionnaire (i.e., no PHI or PII). This survey will be made available at 2 intervals.

In order to establish a benchmark for relapse-free survivorship from which to compare COMP-VA subjects' survivorship, we will be evaluated survivorship of Veterans with a diagnosis of cancers treated with cisplatin using the VA Cancer Registry (or other) which follows Veterans treated in VA for 5+ years following treatment. We will follow current study participants for cancer survivorship for approximately 2-3 years depending on enrollment date and resources available to do so.

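### SAP item 4 names no prognostic covariate for the one-year mortality odds ratio, although cancer type and stage are collected: avoidable loss of precision, not bias

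*SAP*

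**What the plan says.** **Who enters.** Protocol A2 states that "Subjects must be treated for cancer and must provide a reliable hearing test to be enrolled in the treatment arms of this study". None of its listed exclusions concerns tumour type, stage or treatment intent. SAP item 4 narrows the drug, since it expects that "cisplatin patients given the COMP-VA intervention will fair no worse than SOC patients", but it leaves type and stage open.

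**How they are allocated.** Protocol A1 says that "the subject will be randomized to a treatment arm". It gives no allocation ratio and describes no stratification or minimisation. The planned number is "An estimated 320 patients from VA Portland Health Care System (VAPORHCS) receiving chemotherapy".

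**How survival is tested.** Under SAP item 4, the null hypothesis to be rejected is that "COMP-VA patients have lower one-year survival rates than patients treated under SOC". The upper 95% confidence bound of the fitted mortality odds ratio must lie below 1.1. On the model itself the SAP says only: "Analysis for non-inferiority trials using survival outcomes have been described and are easily computed using logistic regression output". No covariate is named. The logistic models for ototoxicity (item 1) and for service use (item 3) each name the arm as their only term.

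**What is collected.** Protocol C3 lists "type of cancer and staging" among the data abstracted from the medical record for each subject with cancer. It does not say as of which date stage is taken.

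**The concern.** Stage and cancer type are likely to be strong predictors of death within a year. If patients of very different prognosis enter one comparison, part of the random variation in the mortality odds ratio comes from chance differences in case mix between the arms. That part can be removed by using baseline factors that the trial already records. The plan as written does not use them.

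Two things are at stake. The first is precision: the interval for a safety outcome is wider than it need be. The second is interpretation. The interval will be wide in any case, so readers will look at the point estimate and ask whether it reflects the mix of stages. The plan gives no prespecified answer. Because item 4 does not list its model terms, covariates could also be chosen after deaths by arm are known.

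**Working it through.** The documents give no event count, power or sample-size derivation for survival, so there is no figure of the plan's own to reproduce.

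**Inputs from the documents:** about 320 patients; margin 1.1 (ln 1.1 = 0.0953); upper 95% bound, sidedness not stated, so both are shown.

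**Assumptions (not in the documents):** 1:1 allocation, so n = 160 per arm; three prognostic groups with shares 40/30/30%; one-year mortality by group of 10/25/60% (strong gradient) or 15/30/50% (milder gradient); true odds ratio 1.

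**Formulas.** Let m be the group mortality, p its mean and Var(m) its variance over the groups.

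- SD of the log OR from case mix alone = sqrt(2·Var(m)/n) / [p(1−p)]
- Unadjusted SE(log OR) = sqrt(2 / [n·p(1−p)])
- Variance ratio, standardised to unadjusted = E[m(1−m)] / [p(1−p)] = 1 − Var(m)/[p(1−p)]
- Chance of passing at true OR 1 = Φ(0.0953/SE − z), with z = 1.96 or 1.645

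**Strong gradient (10/25/60%).**

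- p = 0.04 + 0.075 + 0.18 = 0.295 and p(1−p) = 0.2080.
- Var(m) = 0.13075 − 0.08703 = 0.0437.
- Mix SD = sqrt(2 × 0.0437/160)/0.2080 = 0.112, so a 1-SD imbalance moves the point estimate by a factor of 1.12.
- Variance ratio = 1 − 0.0437/0.2080 = 0.79, a cut of 21%.
- SE falls from sqrt(2/(160 × 0.2080)) = 0.245 to 0.245 × sqrt(0.79) = 0.218.

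**Milder gradient (15/30/50%).**

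- p = 0.06 + 0.09 + 0.15 = 0.300 and p(1−p) = 0.210.
- Var(m) = 0.111 − 0.090 = 0.021.
- Mix SD = sqrt(2 × 0.021/160)/0.210 = 0.077, a factor of 1.08.
- Variance ratio = 1 − 0.021/0.210 = 0.90, a cut of 10%.
- SE falls from 0.244 to 0.231.

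**Weak gradient (two equal groups, 10% and 20%).** Var(m) = 0.05² = 0.0025, p(1−p) = 0.15 × 0.85 = 0.1275, and the cut is 0.0025/0.1275 = 2%. A 1-SD imbalance moves the estimate by a factor of 1.045, and a 1.96-SD imbalance by 1.09.

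**Effect on the non-inferiority test at true OR 1.**

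| Scenario | Bound | Unadjusted | Standardised |
|---|---|---|---|
| 10/25/60% | two-sided 95% | 5.8% | 6.4% |
| 10/25/60% | one-sided 95% | 10.5% | 11.4% |
| 15/30/50% | two-sided 95% | 5.8% | 6.1% |
| 15/30/50% | one-sided 95% | 10.5% | 10.9% |

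With the unadjusted SE of 0.245, the observed OR must be at or below exp(0.0953 − 1.96 × 0.245) = 0.68 (two-sided) or exp(0.0953 − 1.645 × 0.245) = 0.73 (one-sided) to pass.

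**Checks by simulation.** Under the strong gradient, 4,000 simulated trials gave a variance ratio of 0.80 (SE 0.246 to 0.220), in line with the formula. Separate simulations with two stage groups (50% advanced; mortality 10/30% and 10/40%) gave 94–95% coverage for the unadjusted interval.

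**The case against.** A reader might infer that chance imbalance in stage can decide the non-inferiority verdict, because a 1-SD mix shift (1.12 under the strong gradient) exceeds the 1.1 margin. That reading does not hold. The rule acts on the upper confidence bound, not on the point estimate. Starting from an OR of 1, case mix alone would have to move the estimate to 0.68 or 0.73. That is 0.385/0.112 = 3.4 SD (two-sided bound) or 0.308/0.112 = 2.7 SD (one-sided). Failure is by far the likeliest result whatever the stage balance.

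A reader might also take the missing covariates as a flaw in validity. They are not. Imbalance arising by chance after randomisation is part of ordinary sampling variance, and the unadjusted interval already allows for it.

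Three further objections stand in part:

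- **The size is assumed.** With a 10-point gradient at this sample size the gain is negligible.
- **Arm-only is inferred.** Item 4 does not list its terms. The inference from items 1 and 3 is reasonable, but it is not a statement in the plan.
- **Adjustment can change the target.** Putting stage in the model and reading off the arm coefficient gives a conditional odds ratio. In the two-group simulation with 10/40% mortality, its SE rose from 0.261 to 0.279. This counts against using the coefficient, not against a standardised marginal odds ratio, which keeps the meaning of the 1.1 margin and lowers the SE.

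**Conclusion.** The point holds as one of precision and prespecification. The planned analysis is valid, but it leaves unused two baseline factors that the trial already collects and that probably predict one-year death. Under the assumed inputs the variance of the log odds ratio would fall by about 10% to 21%, and by about 2% if mortality differs by only 10 points between two stage groups. These sizes depend on assumed stage shares, stage-specific mortality and 1:1 allocation, none of which the documents give.

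The documents do not support saying that the survival comparison is biased, or that adjustment would rescue it. The chance of passing at a true odds ratio of 1 rises by less than one percentage point. Whether a 1.1 margin is feasible with about 320 patients is a separate and larger question, which adjustment does not settle.

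**What to change.** In SAP item 4:

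1. Prespecify a logistic model for death by one year with arm, grouped cancer stage and grouped cancer type. Take both factors as they stood before randomisation, and say so, because C3 does not fix the date.
2. Average the model predictions over all randomised patients under each arm, and form the marginal COMP-VA versus SOC odds ratio.
3. Obtain its confidence interval by the delta method or the bootstrap, name which, and apply the existing 1.1 rule to the upper bound.
4. Report the unadjusted odds ratio alongside.

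The cost is SAP wording and a few lines of code, with no new data, visits or patients. The one real downside is that sparse cancer types must be grouped in advance, before deaths by arm are seen.

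### Is the 1.1 mortality margin a defect, given that about 320 patients would seldom meet it even if survival is equal?

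*SAP*

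**What the plan says.** Item 4 under Hypotheses to be Tested and Statistical Plan in the SAP calls the survival component a non-inferiority trial: "we require sufficient evidence to reject the null hypothesis that COMP-VA patients have lower one-year survival rates than patients treated under SOC". The margin is a mortality odds ratio of 1.1 for COMP-VA against SOC, estimated by logistic regression, and the test passes only if "the upper 95% confidence bound for the fitted odds ratio must be less than 1.1 to reject the null hypothesis". The SAP does not say whether that bound is one- or two-sided.

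Item 1 of the same section sets the wider aim, that COMP-VA will improve "hearing and quality of life outcomes without diminishing chances for survival". The fourth outcome in the Outcome Measures list, survivorship, is "defined as differences in rates of death during the study period".

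On size, Protocol section A1 says: "An estimated 320 patients from VA Portland Health Care System (VAPORHCS) receiving chemotherapy will be identified by a search". Section C3 adds an estimated 80 subjects per year entering the arms, with no accrual period. Section C3 also plans a registry "benchmark for relapse-free survivorship from which to compare COMP-VA" subjects' survivorship, and continues: "We will follow current study participants for cancer survivorship for approximately 2-3 years depending on enrollment date and resources available to do so".

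**The concern.** A margin of 1.1 on the odds ratio is very tight for a trial of a few hundred patients. If COMP-VA has no effect on survival, which is all item 4 anticipates, the confidence interval will almost always extend well past 1.1 and the test will fail.

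Item 2 of the SAP says COMP-VA may work partly through changes to cisplatin treatment, so survival is the natural counterweight to any hearing benefit, and item 4 is its only randomised test. A failed test would leave the survival part of item 1 without formal support, and a careless reader might take it as a sign of harm.

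The time window also looks unsettled. The outcome definition refers to an undefined study period, item 4 to one year, and Protocol section C3 to 2-3 years.

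**Working it through.** The plan states no power or sample size for survival, so there is no figure to reproduce.

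**Inputs**
- From the SAP: margin 1.1, so ln(1.1) = 0.0953; upper 95% bound from logistic regression. Sidedness is not stated, so both readings are shown (z = 1.960 and 1.645).
- From the Protocol: 320 patients to be identified. At 80 per year, four years of entry would give 320.
- Assumed, because the documents are silent: 1:1 allocation (160 per arm), no loss to follow-up, one-year mortality p between 5% and 50%. The first two assumptions, and treating all 320 as randomised, favour the test.

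**Chance of passing when true mortality is equal**

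SE of the log odds ratio = √(2 / (160·p·(1−p))). Chance of passing ≈ Φ(0.0953/SE − z).

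At p = 50%: SE = √(2/40) = 0.2236 and 0.0953/0.2236 = 0.426. This gives Φ(0.426 − 1.960) = 6.3% two-sided and Φ(0.426 − 1.645) = 11.1% one-sided.

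The exact figures enumerate every pair of death counts and apply the Wald bound, which is what logistic regression with arm as the only predictor gives. Tables with a zero cell count as not passing.

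| Mortality, both arms | SE | Two-sided, exact | One-sided, exact |
|---|---|---|---|
| 5% | 0.513 | 2.9% | 6.6% |
| 10% | 0.373 | 4.0% | 8.0% |
| 20% | 0.280 | 5.2% | 9.5% |
| 30% | 0.244 | 5.9% | 10.1% |
| 40% | 0.228 | 6.2% | 11.5% |
| 50% | 0.224 | 6.6% | 12.0% |

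The chance peaks at 50% mortality, so about 7% and 12% are ceilings at this size. The lower ends depend on the assumed 5%: at 2-3% mortality the exact figures drop to 0.4-1.4% and 2.4-4.7%. With 80 per arm the ranges over 5-50% mortality are 1.2-4.8% and 3.5-8.9%. With 320 per arm they are 4.3-8.6% and 8.0-14.3%.

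**What passing requires**

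With equal observed deaths the upper bound is exp(z·SE). That is 1.55 to 2.73 two-sided, or 1.44 to 2.33 one-sided. If SOC has 48 deaths among 160, COMP-VA may have at most 35 (two-sided) or 37 (one-sided). With 35 deaths the odds ratio is (35·112)/(48·125) = 0.653, the SE is 0.2576, and the two-sided upper bound is 0.653·exp(1.960·0.2576) = 1.08. With 36 deaths the bound is 1.12 and the test fails.

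**Size needed for 80% power at equal mortality**

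n per arm = 2(z + 0.8416)² / (p(1−p)·0.0953²). At p = 50% this is about 6,900 two-sided or 5,400 one-sided. At p = 5% it is about 36,400 or 28,700.

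**Is the test valid?**

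At a true odds ratio of exactly 1.1 with 160 per arm, the exact chance of passing is 1.9-2.6% (two-sided) or 4.6-5.5% (one-sided) over the same mortality range. Those values are close to or below the nominal 2.5% and 5%, so the error that matters for patients is controlled. The rule can also be met if COMP-VA truly lowers mortality. At 30% SOC mortality it passes 84% or 91% of the time at a true odds ratio of 0.5, and 25% or 35% at 0.8.

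**Time window**

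Item 4 tests one-year survival by name. The SAP tracks "audiology rehabilitation service use for one year post-randomization" and contrasts hearing handicap at one year. In Protocol section C3 the 2-3 year follow-up comes directly after the registry benchmark and reads as part of that comparison. The text therefore supports one year for the randomised contrast.

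**The case for a change.** The strongest case for a change is that no reading of the documents brings this test near adequate power under equal survival. Even twice the patients would leave the chance of passing below 15%. A rule meant to show that COMP-VA is no worse passes only when COMP-VA looks clearly better. On that view the plan should make survival an estimation objective, soften the survival part of item 1, and say in advance that failing to exclude 1.1 shows neither harm nor safety. This would be a change of wording, with no new patients or data.

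The arithmetic stands. The case for a change is weaker:
- Estimation would use the same deaths and give the same interval. It removes a label the trial was unlikely to earn, but answers the survival question no better.
- Widening the margin would not help. To have 80% power with 160 per arm it would have to be an odds ratio of 1.77-3.78 (one-sided) or 1.89-4.57 (two-sided), which means about 12-16 percentage points of excess mortality. Nothing in the documents supports accepting that.
- The Outcome Measures section is in the past tense, so deaths may already have been compared by arm. Dropping a pre-specified test at that point would carry its own risk.
- Misreading a failed test as harm is speculation about readers. The reported odds ratio and interval guard against it.
- A hypothesis may be stated even when its test is imprecise, so item 1 can stand.

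**Conclusion.** The concern is right on the numbers but calls for no change. With 320 patients randomised 1:1 and complete one-year vital status, the rule would be met at most about 7% (two-sided) or 12% (one-sided) of the time if survival is equal, whatever the mortality. The figure of 320 counts patients to be identified, so the randomised number may be smaller and the chance lower still.

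This is low power for one listed outcome, in a plan that states no power for it and names no outcome as primary. Followed as written, the rule yields a valid and conservative answer that will probably be inconclusive. A strict margin that may not be met is a defensible trade-off against a loose one that would tolerate a large excess of deaths.

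The open details are ones an analyst can settle sensibly from the text: one-year deaths for the randomised comparison, and a report that says which bound was used and gives the odds ratio with its interval.
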